9.2 Pharmacokinetic Parameter Reporting Specifications

The following parameters will be reported for each study part as applicable, according to the rounding specifications provided in [Table 4](#):

Study Parts 1 and 2:

t_{max} , C_{max} , AUC_{0-t} , AUC_{0-inf} , %AUCextrap, $t_{1/2}$, λ_z , λ_z Lower, λ_z Upper, CL/F, V_z/F , MPR (based on AUC_{0-inf}) and Frel (based on AUC_{0-t} and AUC_{0-inf}).

The following flags/footnotes may be applied to the PK parameters:

Flag	Footnote
a	Rsq of regression was <0.9
b	Period used for regression analysis was less than 2-fold the calculated half-life
c	Extrapolated portion of AUC_{0-inf} >20%

d	Insufficient post- C_{max} data points for estimation of λ_z
e	Entire profile BLQ, no PK parameters could be calculated
f	Quantifiable pre-dose values were observed, however were considered less than 5% of C_{max}

In the event that the R-squared (Rsq) of regression was <0.9 ("a" flag) or the extrapolated portion of $AUC_{0-\infty}$ >20% ("c" flag), then the parameter estimates derived using λ_z and/or $AUC_{0-\infty}$ will be deemed unreliable and will be listed but excluded from the summary statistics and formal statistical analysis.

In the event that the period used for regression analysis was less than 2-fold the calculated half-life ("b" flag) parameter estimates derived using λ_z will be listed, flagged and included in summary statistics and formal statistical analysis.

In the event that quantifiable pre-dose values less than 5% of C_{max} were observed ("f" flag), all parameter estimates for the profiles affected will be listed, flagged and included in summary statistics and formal statistical analysis.

In the event that quantifiable pre-dose concentrations greater than 5% of C_{max} are observed, requirements for further action will be agreed with Genentech and documented at the same time as the PK population.

Additional flags may be applied based on emerging data.

9.2.1 Bioanalytical and Pharmacokinetic Summary Tables

Summary statistics (i.e., mean, SD, coefficient of variation [CV%], median, minimum, maximum and n) will be calculated at each time point for plasma concentration data by treatment.

Imputation of non-numerical values reported in the plasma concentration data (i.e., values that are BLQ) will be entered as zero for the determination of summary statistics.

Summary statistics (i.e., mean, median, SD, CV%, minimum, maximum, n) will be calculated for all plasma PK parameters. Geometric mean, geometric SD, geometric CV% and geometric n will be presented for all PK parameters except t_{max} .

Separate summary tables will be produced for each study part.

9.2.2 Bioanalytical and Pharmacokinetic Figures

Arithmetic mean plasma concentration vs time curves will be produced on a linear/linear scale and error bars for \pm arithmetic SD will be included on the plots.

The arithmetic mean plots will be produced for the following:

- all treatments on the same plot, with separate plots for entrectinib and its metabolite M5
- entrectinib and its metabolite M5 on the same plots, with separate plots for each treatment

Each treatment will be represented on these plots with a different symbol and a legend will be included on the plots to define the symbols used.

Spaghetti plots of individual plasma concentrations against actual sampling times after dosing for each treatment will be produced on both a linear/linear and log10/linear scale. Each subject's concentration profile will be represented on these plots with a different letter or symbol and a legend will be included on the plots to define the letters/symbols used. These data will be plotted for entrectinib and its metabolite M5 on different plots.

Plots of individual plasma concentrations against actual sampling times after dosing for each analyte will also be produced separately for each individual subject with all treatments for that subject overlaid on the same plot. Plots of individual plasma concentrations against actual sampling times after dosing for each treatment will also be produced separately for each individual subject with both analytes for that subject overlaid on the same plot. These plots will be produced on both a linear/linear and log10/linear scale.

For all plots on a linear/linear scale, concentration values reported as BLQ will be set to zero. For all plots on a log 10/linear scale, concentration values reported as BLQ will be set to missing.

Separate figures will be produced for each study part.

9.2.3 Bioanalytical and Pharmacokinetic Listings

The sample collection data (e.g., collection times) for PK samples will be listed. In addition, all plasma concentration data and PK parameters will be listed on a per subject basis. Any flags used will be listed with the appropriate definition.

Separate listings will be produced for each study part.

9.2.4 Statistical Analysis of Pharmacokinetic Parameters

Formal statistical analysis will be performed on the entrectinib and M5 PK parameters C_{max} , AUC_{0-t} and AUC_{0-inf} to assess the relative bioavailability between test and reference formulations. The PK parameters will undergo a natural logarithmic transformation and will be analysed using mixed effect modelling techniques. The model will include terms for treatment, period and sequence fitted as fixed effects and subject nested within sequence fitted as a random effect.

The following pairwise treatment comparisons (*test versus reference*) are of interest in Part 1:

- 600 mg F15 vs 600 mg F06
- 600 mg F16 vs 600 mg F06

The following pairwise treatment comparison (*test versus reference*) is of interest in Part 2:

- 200 mg F06 coarse vs 200 mg F06 fine

If the number of subjects with reliable estimates of AUC_{0-inf} for any period falls below the planned number of evaluable subjects, then consideration will be given as to whether formal statistical analysis will be performed.

The adjusted means including differences from the pairwise comparisons listed above and their associated 90% CIs obtained from the model will be back transformed on the log scale to obtain adjusted GMRs and 90% CIs of the ratios, where the ratio, defined as

test/reference, will be presented. In addition, these will be presented together with the p-value from the pairwise treatment comparison and the intra-subject variability values (denoted as CVw in the results table), where the null hypothesis is defined as no treatment difference.

The intra-subject variability values will be calculated for all treatments combined and are obtained from the residual term from the SAS Software output. These values are calculated as follows:

$$CVw = 100 \times [\exp(\text{Mean Square Error}) - 1]^{1/2}$$

The ANOVA table from the model with F-statistic and p-value for the fixed effects will be presented on a separate page.

The statistical analysis will be performed using actual treatment received and planned sequence as detailed on the randomization schedule. The model will be fitted using the SAS Software procedure PROC MIXED, the method will be specified as Restricted Maximum Likelihood and the denominator degrees of freedom for the fixed effects will be calculated using Kenward and Roger's method [1]. The following is an example of the SAS Software code that will be used:

```
PROC MIXED DATA= METHOD=REML ORDER=INTERNAL;
  CLASS SUBJIDN TRTAN APERIODN TRTSEQPN;
  MODEL LVAR = TRTAN APERIODN TRTSEQPN / OUTP=PRED DDFM=KR;
  RANDOM SUBJIDN(TRTSEQPN);
  ESTIMATE <relevant pairwise treatment comparisons> / CL ALPHA=0.10;
  LSMEANS TRTAN / ALPHA=0.10;
  ODS OUTPUT LSMEANS=MEANS ESTIMATES=EST COVPARMS=CVW;
RUN;
```

where

- LVAR is the natural log transformed PK parameter of interest
- SUBJIDN is the numeric subject identifier variable
- APERIODN is the numeric period variable
- TRTAN is the numeric treatment variable for the actual treatment received
- TRTSEQPN is the numeric sequence variable for the planned sequence received

If there are any deviations from the planned treatment, then the analysis model specified or methods of analysis may be re-evaluated, as appropriate. Details of any deviations from the planned analysis will be documented in the CSR.

For each analysis, distributional assumptions underlying the statistical analyses will be assessed by visual inspection of residual plots. Normality will be examined by normal probability plots, while homogeneity of variance will be assessed by plotting the residuals against the predicted values for the model. If the distributional assumptions for the parametric approach are not satisfied, then additional sensitivity analyses may be performed including the removal of potential outliers or use of non-parametric methods to assess the robustness of the original analysis. In general terms, the results of the original analysis will always be presented in the CSR. This will be documented in the CSR together with the reasoning supporting the most appropriate action taken, if applicable.

9.2.5 Statistical Figures for Analysis of Pharmacokinetic Data

Plots of GMRs obtained from the statistical model will be produced for each of the PK parameters: C_{max} , AUC_{0-t} and AUC_{0-inf} with bars representing the 90% CIs. Plots will include horizontal lines to show representative lower (i.e., 80.00%) and upper (i.e., 125.00%) limits for the ratios.

Separate figures will be produced for each study part and each analyte.

10 Safety Assessments

Safety data summaries will be presented by actual treatment and the safety analysis population will be used throughout.

Separate summary tables and listings will be produced for each study part.

10.1 Extent of Exposure and Treatment Compliance

The number and percentage of subjects dosed with IMP will be presented for each treatment.

Dosing details (including the date and time of all doses administered and any comments) will be listed. Any recorded deviations from the planned dosing treatment will be listed as protocol deviations.

10.2 Meal Details

Meal details, as recorded on the eCRF will be listed. Any recorded deviations from the planned meal times will be listed as protocol deviations.

10.3 Adverse Events

An AE is any untoward medical occurrence in a clinical investigation subject administered a pharmaceutical product, regardless of causal attribution.

Throughout the study, all AEs will be evaluated by the PI and noted in the AE section of the eCRF. AEs will be monitored from the time the subject signs the informed consent form (ICF) until after the final follow-up call in each period and each study part.

AEs will be coded using MedDRA v22.0 (or most recent version) and reported by SOC and PT.

AEs will be classified into the following categories:

- pre-dose AEs: AEs recorded after informed consent has been obtained and prior to the first dose of IMP. Only Serious Adverse Events (SAEs) caused by protocol mandated intervention (e.g., invasive procedures such as biopsies, discontinuation of medications) will be reported
- treatment-emergent adverse events (TEAEs): AEs that commence during/after the first dose of IMP or commence before first dose of IMP (i.e., a pre-dose AE or existing medical condition) but worsen in intensity during exposure to IMP

Where the severity of a pre-dose AE intensifies during/after dosing this will be defined as a new AE and classified as a TEAE.

TEAEs will be assigned to the treatment of the period in which the AE first occurred. Where the severity of an AE intensifies or symptoms change in a subsequent period, this

will be defined as a new AE and included under the treatment associated with the subsequent period. AEs that occur during the washout period will be assigned to the treatment the subject received during the period immediately before the washout period.

An IMP-related AE is any AE where a causal relationship with the IMP is at least a reasonable possibility. When considering their relationship to IMP, AEs will be classified as "YES" (i.e., there is a plausible temporal relationship between the onset of the adverse event and administration of the study drug, and the adverse event cannot be readily explained by the subject's clinical state, intercurrent illness, or concomitant therapies; and/or the adverse event follows a known pattern of response to the study drug; and/or the adverse event abates or resolves upon discontinuation of the study drug or dose reduction and, if applicable, reappears upon re-challenge.) or "NO" (i.e., evidence exists that the adverse event has an etiology other than the study drug [e.g., pre-existing medical condition, underlying disease, intercurrent illness, or concomitant medication]; and/or the adverse event has no plausible temporal relationship to administration of the study drug [e.g., cancer diagnosed 2 days after first dose of study drug]). Pre-dose AEs will always have the classification of "NO" when considering their relationship to IMP.

The severity of AEs will be assessed according to the National Cancer Institute Common Terminology Criteria for Adverse Events (NCI CTCAE, v5.0) grading scale when considering their initial and maximum severity separately. All summary tables will be based on maximum severity but relevant listings will include both initial and maximum severity:

Grade	Severity
1	Mild; asymptomatic or mild symptoms; clinical or diagnostic observations only; or intervention not indicated
2	Moderate; minimal, local, or non-invasive intervention indicated; or limiting age-appropriate instrumental activities of daily living ^a
3	Severe or medically significant, but not immediately life threatening; hospitalization or prolongation of hospitalization indicated; disabling; or limiting self-care activities of daily living ^{b, c}
4	Life-threatening consequences or urgent intervention indicated ^d
5	Death related to AE ^d

^a Instrumental activities of daily living refer to preparing meals, shopping for groceries or clothes, using the telephone, managing money, etc.

^b Examples of self-care activities of daily living include bathing, dressing and undressing, feeding oneself, using the toilet, and taking medications, as performed by subjects who are not bedridden.

^c If an event is assessed as a "significant medical event," it must be reported as a serious AE.

^d Grade 4 and 5 events must be reported as serious AEs.

If the severity or relationship to IMP of a TEAE is missing, the severity/relationship will be tabulated as "missing" in the summary tables.

Where the start date of an AE is missing and the stop date is on or after the day of first dose of IMP or both the start and stop dates are missing then a "worst-case" scenario will be assumed, i.e., the AE is assumed to have occurred post-dose and is therefore considered treatment-emergent. If a partial start date/time is available, then the event will be considered as treatment-emergent unless the partial information suggests otherwise.

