3.2.3 Definition of Visits

For clinical data, visits will be referred to as Day throughout this document and for each study part will be referred to as Screening (Day -28 to -2), Day -1 (Admission) of each treatment period, Day 1 through to Day 5 of each treatment period and Follow-up (12 to 14 days post final dose). Time points within these days are detailed in the schedule of activities in [Appendix 1](#) and in the schedule of PK samples in [Appendix 2](#).

Baseline is defined as the last nominal measurement recorded prior to the first dose of investigational medicinal product (IMP) in each treatment period and each study part.

4 Objectives and Endpoints

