5.1 Brief Description

This is a randomized, open-label, single-center, two-part study in healthy volunteers to explore the performance of entrectinib multi-particulate formulations (Part 1) and the effect of drug substance particle size on entrectinib bioavailability (Part 2).

Part 1

Part 1 is a randomized, open-label, three-treatment, three-period, three-sequence, three-way crossover design. In each treatment period, subjects will receive a single 600 mg oral dose of entrectinib under fed conditions. Entrectinib will be administered as one of three possible formulations:

- Multi-particulate formulation 1: Entrectinib film-coated mini-tablets, 600 mg (240 x 2.5 mg) (Ro 710-2122/F15) (test formulation 1; T1)
- Multi-particulate formulation 2: Entrectinib film-coated mini-tablets, 600 mg (240 x 2.5 mg) (Ro 710-2122/F16) (test formulation 2; T2)
- F06 capsule formulation: Entrectinib (RXDX-101) F06 hard capsules, 3 x 200 mg (Ro 710-2122/F04) (reference formulation; R)

Study treatments will be administered orally within 30 min of consumption of a standardized light "pediatric" breakfast. The composition of the "pediatric" breakfast is as follows:

- 1 hard-boiled egg
- 2 slices of wholemeal bread
- Fruit (e.g., strawberry) jam

The test formulation, provided in a bottle, will be mixed with approximately one tablespoon (~15 mL) of yogurt, which will be swallowed without chewing with approximately 240 mL of water. In each period, palatability (taste and acceptability) of the test formulations will be assessed by completion of a questionnaire shortly after drug administration ([Appendix 3](#)).

The reference formulation will be dosed as 3 × 200 mg capsules, swallowed whole with approximately 240 mL of water.

[figure not shown]
The total duration of the study for each enrolled subject (screening through to end of study) will be up to 10 weeks, divided as follows:

- screening: up to 28 days before the first dose of study drug
- three treatment periods, separated by a treatment-free washout so that there are at least 14 days between each of the three study drug administrations
- safety follow-up phone call: 12 to 14 days after the last dose of study drug

Subjects will be resident in the clinic from the morning of Day -1 until at least Day 3 in each treatment period. Subjects will also have ambulatory clinic visits at screening, and Days 4 and 5 in each treatment period.

[Figure 1](#) presents an overview of the study design.

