10.4.1 Summary Tables for Laboratory Evaluations

Hematology and coagulation, and serum biochemistry will be summarized (mean, SD, median, minimum, maximum and n) for each laboratory parameter at each time point, including changes from baseline (Day -1, Admission in each study period) at each 96 h post-baseline time point by treatment.

Shift tables from baseline to each post-baseline time point (with respect to the number and percentage of subjects with values below, within or above the reference range) will be presented by treatment. Percentages will be based on the number of subjects with measurements at baseline and the relevant 96 h post-baseline time point.

Reference ranges for each laboratory parameter will be presented for the relevant parameter in each summary table.

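### The SAP assigns TEAEs by period and attaches Day -1 to each period, so an event between admission and dosing in Period 2 or 3 most naturally falls under a formulation not yet taken (minor)

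*SAP*

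**What the plan says.** SAP section 10.3 gives three attribution rules for treatment-emergent events:

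- New events: "TEAEs will be assigned to the treatment of the period in which the AE first occurred".
- An event that intensifies or changes in a later period "will be defined as a new AE and included under the treatment associated with the subsequent period".
- Washout: "AEs that occur during the washout period will be assigned to the treatment the subject received during the period immediately before the washout period".

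The same section divides events by time. Pre-dose events are "AEs recorded after informed consent has been obtained and prior to the first dose of IMP". TEAEs include "AEs that commence during/after the first dose of IMP or commence before first dose of IMP" when the latter worsen on exposure.

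Section 10.3 does not say when a period or a washout starts and ends. The nearest wording is elsewhere in the SAP:

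- Section 3.2.3 names the visits as "Day -1 (Admission) of each treatment period, Day 1 through to Day 5 of each treatment period".
- Section 5.1: "Subjects will be resident in the clinic from the morning of Day -1 until at least Day 3 in each treatment period".
- Section 10.4.1 summarises laboratory "changes from baseline (Day -1, Admission in each study period").

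Section 5.1 describes the washout as what separates the treatment periods, with doses at least 14 days apart.

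**The concern.** In a crossover, an event before the Period 2 dose can follow only the Period 1 product. If Day -1 belongs to Period 2 and attribution goes by period, that event is entered under the Period 2 product, which has not been given. The same applies to an ongoing event that worsens between admission and dosing.

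Incidence and severity of adverse events form part of the secondary endpoints (SAP section 4.2.2), and every summary in sections 10.3.1.1 to 10.3.1.7 is by treatment. These include the tables of IMP-related events, events of special interest and serious events. If such an event kept the subject from being dosed, it would be charged to a treatment never received, although section 10 presents safety data by actual treatment.

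The window contains scheduled checks. The schedule of activities puts laboratory tests and a symptom-directed physical examination on Day -1, and an ECG and vital signs before dosing on Day 1. An abnormality first found there might be given an onset date inside the window. How such onsets are dated is not stated, so that is an assumption.

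**Working it through.** The plan gives no figure on this point to reproduce. The check sets the wording side by side and then counts the exposure.

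**Is an event on Day -1 of Period 2 a TEAE?** It follows the subject's first dose, given in Period 1, so on the plain reading of section 10.3 it is a TEAE and not a pre-dose event. Protocol section 5.3.1 requires all adverse events to be reported once study drug has started, so it is collected.

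**Which column does it enter?** Three readings are possible.

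1. *The period starts at admission.* Sections 3.2.3, 5.1 and 10.4.1 all attach Day -1 to the period. Washout separates periods, so it ends at admission. The event goes to the formulation about to be given.
2. *Washout lasts until the next dose.* The event goes to the preceding formulation, which is the correct result. No sentence states this.
3. *First dose is read per period*, as in the baseline definition in section 3.2.3. The mock listing of pre-dose events, which is to continue for all periods and treatments, leans this way. The event becomes a pre-dose event. Section 10.3 then always classes it as unrelated, and section 10.3.1 leaves it out of the summary tables. That is a different defect.

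Only reading 2 gives a correct table. Reading 1 has the most support in the text.

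**How many windows are there?** Inputs are from SAP section 5.3: Part 1 has 15 subjects, three periods and 5 subjects per sequence; Part 2 has 16 subjects, two periods and 8 per sequence. Full completion is assumed.

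- Windows = subjects × (periods − 1).
- Part 1: 15 × 2 = 30. Part 2: 16 × 1 = 16.

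**How long is a window?** The time from admission to dosing is not given. I assume 24 h, with a range of 20 to 28 h.

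| Window | Share of a 14-day (336 h) interval | Part 1 subject-days (30 × h/24) | Part 2 subject-days (16 × h/24) |
|---|---|---|---|
| 20 h | 20/336 = 6.0% | 25 | 13.3 |
| 24 h | 24/336 = 7.1% | 30 | 16 |
| 28 h | 28/336 = 8.3% | 35 | 18.7 |

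These are shares of time, not of events. Fourteen days is the minimum interval, so for a given window length the share is an upper limit.

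**In which direction would events move?** The Part 1 sequences T1T2R, T2RT1 and RT1T2 contain only the transitions T1 to T2, T2 to R and R to T1. Each occurs in two sequences of 5 subjects, giving 10 windows. Misassigned events can move only from F15 to F16, from F16 to the F06 capsule, or from the capsule to F15. Between any two formulations they cannot cancel.

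**What is the largest effect of one subject on a column?** Part 1: 1/15 = 6.7 percentage points. Part 2: 1/16 = 6.3 points (6.25).

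**The case against.** A reader might infer that the SAP lays down a definite rule that gives the wrong attribution. The documents do not support that. Section 3.2.3 is a convention for naming visits and does not define where a period begins for adverse-event purposes. Mock listings for pregnancy tests and haematology print the Period 2 Day -1 row against the Period 2 product, but they are not adverse-event listings, and section 16 says the mocks are illustrative. Section 5.1 calls the washout treatment-free and expresses it through the interval between doses, so a programmer could reasonably treat it as lasting until the next dose. All of this stands: the boundary is undefined. It does not remove the point, because the correct reading is nowhere stated and other wording points against it.

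A reader might also infer that events elicited at re-admission are generally misassigned. They are not. The rule works on onset, so an event reported at admission that began earlier, after the end of the preceding period, already goes to the preceding treatment. Only onset, worsening or change inside the window is affected.

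Nor does a misassigned event automatically lower one incidence and raise another. Section 10.3.1 counts each subject once per treatment at each level, so a column changes only if the subject has no other qualifying event there.

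Finally, the consequence is small. With a half-life of 20 to 30 h (protocol section 1.1.2.2), 13 days (312 h) after a dose is 312/30 = 10.4 to 312/20 = 15.6 half-lives, leaving under 0.1% of the drug. An event starting then is unlikely to say much about either formulation. The investigator judges relatedness separately, and the mock adverse-event listing carries onset date and time, so a misplaced event would be visible. This stands and limits the severity.

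**Conclusion.** The point holds as a minor one. The attribution rule is tied to an unbounded period instead of to a dose, and its most natural reading puts events from the hours before dosing in Period 2 or 3 under a formulation not yet taken. The exposure is 30 windows in Part 1 and 16 in Part 2, assuming full completion and about 24 h per window. No event rate can be derived from the documents, and few events are expected. The shifts of 6.7 and 6.3 points are conditional maxima for one subject in one column. Only the descriptive safety summaries by formulation are affected; the primary pharmacokinetic analysis is not.

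**What to change.** Replace the period rule in SAP section 10.3 with one based on dosing: assign each new or worsened TEAE to the last IMP dose taken before its onset, using actual dosing date and time. State that washout runs until the next dose, so that events before dosing in Periods 2 and 3 go to the preceding formulation. For consistency, add that the first dose in the pre-dose and TEAE definitions means the subject's first dose in the study part; this closes the third reading.

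The cost is a few sentences and a date-time comparison in the programs. No new data are needed: section 10.1 already lists dose date and time, and the mock adverse-event listing already holds onset date and time.
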